Sample size calculation

Normal distribution model: $x=Z(c/100)^2 r(100-r)$. $n=Nx/((N-1)E^2+x)$ $E=\text{Sqrt}[(N-n)x/n(N-1)]$. With a margin of error of 5%, a confidence level of 95%, with a prevalence of migraine in the general population of the State of San Luis Potosi of 271800 with a distribution response of 15%.¹⁹ The recommended sample size is 196 participants. Due to the fact that a pilot study will be conducted, 10% of the sample size will be taken to make it representative, a sample size of 20 participants for each group is decided.²⁰

Descriptive statistical analysis of the variables of interest will be performed. For continuous variables, analysis will be performed using the Student's t-test. The number of participants (n) and the final analysis was calculated using R (56). Alpha, the probability of type 1 error was set to 0.05 and the power was set to 0.8 which resulted in the probability of a type 2 error of 0.2, given that we limited to 20 participants per treatment, delta was estimated with this restriction.

ETHICS

Risk category: Risk greater than minimal.

Authorization will be requested from the Research Ethics Committee of the Hospital Central "[name] Prieto". The study will be performed according to the Mexican Official Standard for the conduct of clinical studies in humans NOM-012-SSA3-2012²¹, and international standards (Declaration of Helsinki²² and International Harmonized Guide (ICH) of Good Clinical Practices²³) The diagnostic maneuvers that will be used are considered of higher than minimal risk because it is an interventional study according to article 17 of the regulations of the General Law of Health²³ on Health Research.

In addition, it is a priority to safeguard the physical and mental integrity of the patient, and privacy is respected by maintaining the confidentiality of the data at all times during the research, as well as the data obtained at the end of it. The consent of the legal subjects will be obtained through a document specifying the objective of the study, the duration, as well as the methods and medications that they will receive randomly.

RESULTS

Eighty-seven patients were evaluated, of which only 33 patients were included in the study. In the Memantine group with 16 patients and 17 in the Sodium Valproate (VPA) group; only 27 patients concluded the study.

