Demographic data: In the Memantine group there were 13 women and three men, in the VPA group 13 women and four men. The average age of the patients in the Memantine group was 31.18 ± 10.94 years and those in the VPA group 31.58 ± 7.51 years ([Table 1](#)).

Migraine characteristics: In the Memantine group 62.5% (n=10) had a family history of migraine and in the VPA group 52% (n=9). The age of migraine onset in both groups was 18 years on average. Headache pain characteristics in the memantine group were pulsatile in 81.25% (n=13), hemicranial 87.5% (n=14), disabling activities of daily living 93.75% (n=15), with photophobia in 87.50% (n=14), sonophobia 100% (n=16), disabling activities of daily living 93.75% (n=15), nausea and vomiting in 87.5% (n=14) in the VPA group was pulsatile in 76.47% (n=13), hemicranial 76.47% (n=13), disabling activities of daily living in 94.12% (n=16) with photophobia in 94.12% (n=16), sonophobia 58.82% (n=10), nausea and vomiting in 100% (17). With respect to aura only present in three patients in the memantine group and in four in the VPA group. ([Table 1: Migraine characteristics](#).)

Primary objective: In the Memantine group with average migraine attacks before treatment of 5.31 (SD+1.54) per month in the three months before and after three months of treatment 0.93 (SD+1.49) per month, with a decrease of 4.21 (SD+1.76) migraine attacks $p <<0.001$ ([Figure 1](#)). ([Figure 1](#)). In the VPA group with pretreatment mean migraine attacks of 5.35 (SD+1.11) and after three months of treatment of 0.77 (SD+1.16) ([Figure 2](#)) with a decrease of 4.5 (SD+1.39) migraine attacks $p <<0.001$ ([Figure 3](#)).

[figure not shown]
[figure not shown]

[figure not shown]
Table 1 . Baseline characteristics of both groups.

Variable	Memantine	Sodium Valproate
Sex (%)		
Woman	13 (81.25%)	13 (76.47%)
Man	3 (18.75%)	4 (23.52%)
Average age	31.18 ± 10.94	31.58 ± 7.51
Family history of migraine (%)	10 (62.5%)	9 (52.94%)
Characteristics of migraine		
Type of pain (%)		
Pulsating	13 (81.25%)	13 (76.47%)
Oppressive	3 (18.75%)	4 (23.52%)
Pain location (%)		
Hemicranial	14 (87.5%)	13 (76.47%)
Holocranial	2 (12.5%)	4 (23.52%)
Photophobia No. (%)	14 (87.50%)	16 (94.12%)
Sonophobia No. (%)	16 (100%)	10 (58.82%)
Nausea and vomiting No. (%)	14 (87.5%)	17 (100%)
Incapacitates activities of daily living	15 (93.75%)	16 (94.12%)
Migraine without aura	13 (81.25%)	13 (76.47%)

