Migraine with aura	3 (18.75%)	4 (23.52%)

Secondary objectives. - Treatment response rate which is referred to as the decrease of equal or more than 50% of migraine days. In the Memantine group with pretreatment migraine days 4.3 (SD+ 1.93) and post treatment 0.23 (SD+ 0.44) with a mean decrease in migraine days of 3.9 (SD+ 1.89) $p <<0.001$. In the Sodium Valproate group with pretreatment migraine days 5.5 (SD+ 1.25) and post treatment 0.27 with mean decrease of migraine days 4.88 with (SD+ 1.29) $p <<0.001$ ([Figure](#))

4). In both groups the 27 patients presented a successful treatment response rate, in the Memantine group with a decrease in percentage of migraine days average 94% (SD+ 9.95) and in the Sodium Valproate group 93.18% (SD+ 14.50).

The intensity of migraine was evaluated with the Visual Analog Scale (VAS) pre and post treatment. In the Memantine group pre-treatment VAS 8.5 (SD+ 1.36) and post-treatment 4.28 (3.65) $p < 0.00014$. In the VPA group with pretreatment VAS 8.94(SD+ 0.87) and post treatment 2.5 (SD+ 0.87) $p < 0.0000012$.

Migraine disability assessed with MIDAS in the Memantine group with MIDAS mean pretreatment 60.87 (SD+ 25.22) and post-treatment 15.57 (SD+ 14.32) $p < 0.000004$. In the Sodium Valproate group with MIDAS pretreatment of 51.92 (SD+ 22.67) and post treatment 10.53 (SD+ 19.97) $p < 0.00002$ ([Figure 5](#)).

Figure 5. MIDAS pre- and post-treatment in both groups.

Side effects: The side effects presented by the patients were not severe in their totality, eight patients in the Memantine group presented non-severe side effects and seven patients in the sodium valproate group ([Table 2](#)), the most frequent in both groups being somnolence.

Table 2 . Side effects

	Memantine	Sodium Valproate
None		
Drowsiness		
Lack of concentration		0
Parasomnia	0	1
Dizziness		0
Total		

DISCUSSION

This is the first randomized double-blind pilot clinical trial comparing the efficacy and safety of memantine with a first-line treatment, sodium valproate.

With the objective of recruiting 40 patients as a pilot study, the Neurology outpatient clinic was suspended due to the COVID-19 pandemic, we finally managed to recruit 33 patients, 3 lost follow-up and 3 dropped out of the study due to COVID-19 and only 27 patients were included.

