Being a carrier of systemic disease (infectious, immunological, or metabolic processes) or cardiovascular (myocardial, coronary, or valvular disease) prevents their participation in the study.

Primary outcomes

The primary outcome was the difference in change from baseline in the monthly attack frequency at week 12 between the two groups (using migraine diary).

Secondary outcomes

1. Evaluate the response rate to treatment.
2. Evaluate migraine disability using MIDAS (Migraine Disability Assessment) before and after treatment.
3. Identify adverse effects to sodium valproate and memantine.

Statistical analysis.

Statistical analysis

Descriptive statistical analysis of the variables of interest will be carried out.

For continuous variables, their research will be analyzed using the t-student test.

First, the number of participants (n) and the final analysis were calculated using R (56).

Alpha, the probability of a type 1 error was set to 0.05.

The power was set to 0.8, resulting in a type 2 error of 0.2.

Since we were limited to 20 participants per treatment, the delta was estimated with this restriction.

Since we were limited to 20 participants per treatment, the delta was estimated with this restriction.

Results

Table 1. Baseline Demographic and Clinical Characteristics

[figure not shown]
Characteristic	Memantine	Sodium Valproate	p
Female sex – no (%)	13(81.25%)	13 (76.47%)	
Male sex – no (%)	3 (18.75%)	4 (23.52%)	0.54*
Age	$31.18 \pm 10.94^{\$}$	$31.58 \pm 7.51^{\$}$	0.91*
A family history of migraine (%)	10 (62.5%)	9 (52.94%)	0.82*
Clinical characteristics			
Photophobia - no (%)	14 (87.50%)	16 (94.12%)	0.48*
Phonophobia - no (%)	16 (100%)	10 (58.82%)	0.60*
Nausea - no (%)	14 (87.5%)	17 (100%)	0.23*
Disability activities of daily living	15 (93.75%)	16 (94.12%)	0.74*
Migraine without aura	13 (81.25%)	13 (76.47%)	0.54*
Migraine with aura	3 (18.75%)	4 (23.52%)	

* Fisher's exact test

§ Plus-minus values are means \pm SD

PRIMARY OUTCOME

[figure not shown]
Monthly attack migraine frequency before and after treatment

Secondary outcome

Evaluate the response rate to the treatment

Figure 2. Days with migraine before and after treatment

Adverse Events

Table 2. Adverse Events According to Group

	Memantine (n=17)	Sodium Valproate (n=16)	Clinical severity CTCAE*
Any adverse event	8	7	
Somnolence	4	6	Grade 1-Mild
poor concentration	2	0	Grade 1-Mild
Parasomnia	0	1	Grade 1-Mild
Dizziness	2	0	Grade 1-Mild

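### Three reporting errors: the SAP Table 1 p-value for phonophobia (0.60) does not follow from its counts and sits in an unlabelled one-sided column; SAP Table 2 reverses the arm sizes; adverse effects are called infrequent in one document and frequent in the other

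*SAP*

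**What the plan says.** **Baseline table.** SAP Table 1 gives, in the row "Phonophobia - no", 16 (100%) on memantine and 10 (58.82%) on valproate, p = 0.60. The p-values carry a footnote naming "Fisher's exact test", with no statement of one- or two-sided. The protocol Results give the same counts: "sonophobia 100% (n=16" for memantine and "sonophobia 58.82% (n=10" for valproate. Protocol Table 1 repeats them. The protocol Discussion describes the two groups as very alike, clinical characteristics included.

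**Arm sizes.** The protocol Results say "In the Memantine group with 16 patients and 17 in the Sodium Valproate (VPA) group". SAP Table 2 heads its columns the other way round: "Memantine (n=17" and valproate with 16.

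**Adverse effects.** The protocol Results report "eight patients in the Memantine group presented non-severe side effects and seven patients in the sodium valproate group". SAP Table 2 has the same 8 and 7 under the same arm names, all graded mild. The protocol Summary, which defines safety by the frequency and severity of adverse events, calls the effects infrequent. The SAP Conclusions call them frequent.

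**The concern.** A split of 100% against 59% in arms of 16 and 17 cannot yield a p-value of 0.60. It is the largest baseline difference in the table (41 points), and the printed value presents it as unremarkable beside a statement that the groups were clinically alike. One failing row also raises the question of how the rest of the column was computed.

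The Table 2 headings set the denominators for the safety result, so reversed headings give wrong per-arm rates. Frequency of adverse events is half of the trial's own definition of safety, and on that half the two documents reach opposite conclusions from identical counts.

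**Working it through.** **1. Phonophobia.** Inputs: 16 of 16 and 10 of 17 (SAP Table 1; protocol Results and Table 1). In total 26 patients had phonophobia and 7 did not. With margins fixed:

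- All 7 without phonophobia in the valproate arm (as observed): C(17,7)/C(33,7) = 19,448/4,272,048 = 0.0046. This is the upper tail.
- All 7 in the memantine arm: C(16,7)/C(33,7) = 11,440/4,272,048 = 0.0027. This is the only other table no more probable than the observed one.
- Two-sided Fisher: 0.0046 + 0.0027 = 0.007. The lower tail is 1.00.
- Chi-square gives 0.0038, or 0.0137 with continuity correction.
- With the Table 2 sizes (16/17 vs 10/16), Fisher gives 0.039 two-sided and 0.035 or 0.997 one-sided.

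None of these is 0.60.

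**2. The rest of the column.** The same test on every categorical row, with arms of 16 and 17. The lower tail is the probability of a memantine count at or below the one observed.

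| Row | Memantine vs valproate | Printed p | Lower tail | Upper tail | Two-sided |
|---|---|---|---|---|---|
| Male sex | 3 vs 4 | 0.54 | 0.537 | 0.775 | 1.00 |
| Family history | 10 vs 9 | 0.82 | 0.818 | 0.420 | 0.73 |
| Photophobia | 14 vs 16 | 0.48 | 0.477 | 0.897 | 0.60 |
| Phonophobia | 16 vs 10 | 0.60 | 1.00 | 0.005 | 0.007 |
| Nausea | 14 vs 17 | 0.23 | 0.227 | 1.00 | 0.23 |
| Daily activities | 15 vs 16 | 0.74 | 0.742 | 0.773 | 1.00 |
| With aura | 3 vs 4 | 0.54 | 0.537 | 0.775 | 1.00 |

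Six of the seven rows match the lower tail. Nausea matches two-sided as well; the other five do not. For family history the printed value is the larger tail, so the column does not simply report the smaller tail. Phonophobia is the only row that matches nothing.

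Age also carries the Fisher mark, although it is a mean and SD. A t-test on 31.18 (SD 10.94) and 31.58 (SD 7.51) has pooled SD √[(15 × 10.94² + 16 × 7.51²)/31] = 9.33 and t = −0.40/(9.33 × √(1/16 + 1/17)) = −0.12. This gives p = 0.90, close to the printed 0.91.

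**3. Arm sizes.** In SAP Table 1, 13 women are 81.25% on memantine (13/16) and 76.47% on valproate (13/17). The sexes add to 13 + 3 = 16 and 13 + 4 = 17. Seventeen valproate patients with nausea cannot come from an arm of 16. So the Table 2 headings conflict with the SAP's own Table 1 as well as with the protocol.

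The event counts do follow the arm names. SAP Table 2 adds to 4 + 2 + 0 + 2 = 8 on memantine and 6 + 0 + 1 + 0 = 7 on valproate, which agrees with the protocol Results.

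**4. Adverse-event rates.**

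| Denominators | Memantine | Valproate | Difference | Fisher, two-sided |
|---|---|---|---|---|
| 16 and 17 (all randomised) | 8/16 = 50% | 7/17 = 41% | 9 points | 0.73 |
| 17 and 16 (as headed) | 8/17 = 47% | 7/16 = 44% | 3 points | 1.00 |

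Overall, 15/33 = 45% (exact 95% CI 28% to 64%).

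**The case against.** The best case on the other side is that nothing in the trial turns on these errors. Phonophobia is neither an outcome nor a listed confounder. The counts stand beside the faulty p-value, so a reader can see the gap. The swapped headings move each arm by about 3 points and keep the order. Event counts and severity agree across the documents. Neither document sets a threshold for frequent or infrequent, so that conflict is one of wording. All of this stands, and it is why the point is a reporting correction and no more.

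It can also be said that the footnote never claims a two-sided test, and that on the tail the other rows follow, phonophobia would have read 1.00 and concealed the imbalance even better. That is correct. It shows that replacing one number is not enough: a one-sided column cannot serve as a check of comparability in both directions. The Fisher mark on age may be a symbol lost in reading the PDF, so it calls for a label and is not counted as a separate error.

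Three stronger readings are tempting, and the documents support none of them:

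- **A reader might infer that randomisation failed or that the efficacy comparison is confounded.** With seven categorical rows, a crude multiplicity adjustment gives 7 × 0.0072 = 0.05, and nothing in the documents links phonophobia to the change in attack frequency.
- **A reader might infer that memantine caused more adverse events.** The 9-point difference rests on 8 and 7 patients, with p = 0.73.
- **A reader might infer that the treatment labels in Table 2 are swapped.** The events stay with the same arm names in the protocol Results; only the sizes in the headings conflict.

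**Conclusion.** All three errors hold.

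- The phonophobia p-value is wrong for its printed counts: 0.007 two-sided against 0.60. The documents do not show whether the counts or the p-value is at fault, so 0.007 is conditional on 16/16 and 10/17 being confirmed. The other categorical values are unlabelled one-sided tails, and the column is not the two-sided comparison a reader would assume.
- The Table 2 headings are reversed relative to every other source of arm size in the two documents.
- The two statements on how common adverse effects were contradict each other. At 45% of randomised patients, the bare word infrequent is hard to defend, but the plan sets no cut-off that would decide it.

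The 50% and 41% assume that all randomised patients form the safety denominator. The protocol Work Plan randomises at recruitment and hands out drug at the week 4 visit, so the number treated could be smaller. The primary comparison is unaffected, and no adverse-event difference between arms is shown.

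**What to change.** 1. **SAP Table 1.** Verify the phonophobia counts against source. Then either recompute the whole column as two-sided Fisher and say so, or drop the baseline p-values. On the printed counts the two-sided values are: sex 1.00, family history 0.73, photophobia 0.60, phonophobia 0.007, nausea 0.23, daily activities 1.00, aura 1.00. Label age as a t-test.
2. **Protocol Discussion.** If the counts stand, qualify the statement that the groups were very alike in clinical characteristics by giving phonophobia as 100% vs 59%.
3. **SAP Table 2.** Confirm the arm sizes from the randomisation records and the numbers treated from the dispensing records. Correct the headings, state which denominator is used, and add percentages (8/16 = 50% and 7/17 = 41% if all randomised patients are counted).
4. **Protocol Summary and SAP Conclusions.** Replace both adjectives with one identical sentence giving the counts (8 and 7 patients), the confirmed percentages and the mild grading.

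The cost is edits to two tables and a few sentences, plus one check of source and randomisation records. No new data and no outcome analysis are needed.

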Recruitment was carried out from July 2019 to August 2020 in the outpatient service of Neurology, Referral and Emergency of the Central Hospital. Patients who met the inclusion criteria and signed the informed consent form participated in the study. At the time of recruitment, they will be randomized by computer by an external collaborator of wide experience, assigning them a number and an external collaborator will distribute them in one of the two groups. Double-blinding will be performed, both for the researcher and for the participant, the only one who knew which group they were assigned to was the one who performed the randomization.

A total of 4 visits were made, with a time interval of one month for each visit.

Visit 1 (Week 0): a clinical history was taken, a physical examination was performed, the informed consent form was signed (Annex 1), and the inclusion and exclusion criteria form (Annex 2) was filled out by the researcher. A "Migraine diary" (Annex 3) was provided to the patient where the migraine attacks were recorded to identify the baseline characteristics such as frequency, intensity, duration.

Visit 2 (Week 4): the patient was given the medication assigned by the corresponding randomization. Memantine or VPA was prescribed as an oral tablet at night for one week and then increased in the second week to one tablet in the morning and at night. The baseline MIDAS survey was performed to identify migraine disability. The baseline "Migraine Diary" was collected and a new "Migraine Diary" was provided.

Visit 3 (Week 8): Frequency of migraine attacks, adverse effects and tolerability of treatment were assessed by the investigator. The "Migraine Diary" was collected and a new "Migraine Diary" was provided. The corresponding medication was given for four weeks.

Visit 4 (Week 12): Visit 3 (Week 8): Migraine attack frequency, adverse effects and tolerability of treatment were assessed by the investigator. The "Migraine Diary" was collected and a new "Migraine Diary" was provided. The corresponding medication was given for four weeks.

Visit 5 (Week 16): Frequency of migraine attacks, adverse effects and tolerability of treatment were evaluated by the investigator. The "Migraine Diary" was collected. The MIDAS survey was performed again to assess post-treatment disability.

Financing

A donation of the pharmacological treatment Memantine and sodium Valproate was received from the Torrent Pharma Laboratory (Annex 5).

STATISTICAL ANALYSIS

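### SAP Table 2 heads its adverse-event counts with denominators totalling all 33 randomised patients (with the arm sizes transposed), and these are not shown to be the patients exposed to drug

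*SAP*

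**What the plan says.** SAP, Results, Table 2 lists patients with any adverse event and four specific events by arm, under the headers "Memantine (n=17") and "Sodium Valproate (n=16"). It prints counts only, with no percentages, risk difference or test.

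The Protocol's Results give the allocation as "In the Memantine group with 16 patients and 17 in the Sodium Valproate (VPA) group", and report that "eight patients in the Memantine group presented non-severe side effects and seven patients in the sodium valproate group". The Summary gives 14 memantine and 13 valproate completers. The Discussion accounts for the rest: "3 lost follow-up and 3 dropped out of the study due to COVID-19 and only 27 patients were included". It does not say when they left.

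On timing, the Protocol's Work Plan randomises patients at recruitment. The first tablets come at Visit 2 (week 4), where "the patient was given the medication assigned by the corresponding randomization". At the same visit, "The baseline MIDAS survey was performed to identify migraine disability". Adverse effects are listed for assessment at Visits 3, 4 and 5 (weeks 8, 12 and 16).

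Neither document defines a safety population or states how many patients took a dose.

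**The concern.** An adverse drug effect can occur only in someone who took the drug, and is reliably recorded only in someone who was then asked about it. Here at least four weeks separate randomisation from the first dose, and another four separate the first dose from the first scheduled assessment. A patient who left in the diary month could not have a drug effect. One who left between weeks 4 and 8 missed every scheduled assessment. Either could sit in a denominator of 33 as event-free.

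The losses are unequal (2 against 4), so any such dilution need not be the same in both arms. The Protocol's Elimination Criteria also remove patients who cannot tolerate titration. Titration falls in the first two weeks on drug, before week 8, and no count of such removals is given.

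Safety is a stated objective, which the Protocol's Summary says is measured by the frequency and severity of adverse events, and a frequency needs a denominator. The two documents describe adverse effects in opposite terms: infrequent in the Protocol's Summary, frequent in the SAP's Conclusions.

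**Working it through.** **1. Do the printed headers match the allocation?**
- Total: 17 + 16 = 33, the number included in the Protocol's Results.
- By arm they do not match. The Protocol has 16 memantine and 17 valproate. SAP Table 1 agrees with the Protocol: 13/16 = 81.25% (memantine women) and 13/17 = 76.47% (valproate women).
- The headers are therefore transposed. With 16 patients allocated to memantine, 17 cannot be its dosed count.
- The event rows add up: 4 + 2 + 0 + 2 = 8 (memantine) and 6 + 0 + 1 + 0 = 7 (valproate).

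**2. Who left?** Memantine 16 - 14 = 2; valproate 17 - 13 = 4; total 6, matching the Discussion's 3 + 3.

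**3. Any adverse event under the three denominators the documents supply**

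| Denominator | Memantine | Valproate | Difference (points) | Fisher p |
|---|---|---|---|---|
| As printed | 8/17 = 47.1% | 7/16 = 43.8% | +3.3 | 1.00 |
| Randomised | 8/16 = 50.0% | 7/17 = 41.2% | +8.8 | 0.73 |
| Completers | 8/14 = 57.1% | 7/13 = 53.8% | +3.3 | 1.00 |

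**4. Range over every possible dosed count.** Assumption: all completers were dosed and any subset of the six leavers may have been, so memantine is 14 to 16 and valproate 13 to 17 (3 x 5 = 15 combinations). The event counts stay at 8 and 7. Difference = 100 x (8/memantine n - 7/valproate n):

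| Memantine n | Valproate 17 | 16 | 15 | 14 | 13 |
|---|---|---|---|---|---|
| 16 | +8.8 | +6.3 | +3.3 | 0.0 | -3.8 |
| 15 | +12.2 | +9.6 | +6.7 | +3.3 | -0.5 |
| 14 | +16.0 | +13.4 | +10.5 | +7.1 | +3.3 |

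The difference is negative in 2 of 15 cells. Both need all four valproate leavers to be undosed, with at most one undosed memantine leaver. Fisher p is 0.48 to 1.00 throughout. For somnolence (4 against 6) the difference runs from 4/16 - 6/13 = -21.2 to 4/14 - 6/17 = -6.7 points (p 0.27 to 1.00), so its direction does not change.

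**5. Is there indirect evidence on who reached Visit 2?** MIDAS is a sum of days, so a group mean must be a whole number divided by n. The Protocol's Results read "In the Sodium Valproate group with MIDAS pretreatment of 51.92".
- Valproate 51.92 fits n = 12 (623/12 = 51.917, rounded), n = 13 (675/13 = 51.923, rounded or truncated) and n = 14 (727/14 = 51.929, truncated). It does not fit 17 (882/17 = 51.88, 883/17 = 51.94), nor 15 or 16.
- Memantine 60.87 fits n = 15 (913/15 = 60.867, rounded) or n = 16 (974/16 = 60.875, truncated). It does not fit 14 (852/14 = 60.86, 853/14 = 60.93).

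So 3 to 5 of the 17 valproate patients are absent from the reported baseline MIDAS mean, against 0 or 1 of the 16 memantine patients. The mean does not say why.

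**The case against.** A reader might infer that the denominator is known to differ from the number dosed. The documents do not show this. All six may have left after Visit 2, in which case 16 and 17 are the dosed counts and, beyond the transposition, only the week-8 question remains. This part of the objection stands.

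A reader might also take the valproate MIDAS mean as proof that three or more patients never started drug. It is not. Thirteen is both the completer count and the only size that fits under rounding and truncation alike, so a completer-only summary is a plain explanation. That rule cannot have been used in both arms, because the memantine mean does not fit its 14 completers, but inconsistent summarising is not evidence of undosed patients. There is contrary evidence too. The baseline diary was collected at Visit 2, and of the sizes 12 to 17 only 17 fits both the valproate baseline attacks (5.35 = 91/17) and VAS (8.94 = 152/17). If those are diary values, all 17 reached dispensing. That is not conclusive either, since the Results describe the memantine baseline as covering the three months before treatment, which points to a history. The MIDAS mean is a reason to check, no more.

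Finally, a reader might infer that the safety comparison reverses. Table 2 prints only counts, the conclusions describe both groups together, all events are grade 1, and the sign changes only at one corner of the range. No stated conclusion depends on the denominator. What survives is that counts under an n are read as a fraction of that n, and that the n printed for memantine exceeds the number allocated to it.

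**Conclusion.** The point holds as a defect in the safety population and its reporting. The Table 2 headers total all randomised patients, are transposed between arms, and are not shown to be patients exposed to drug. With the dosed count unknown, the any-event difference is fixed only to within -3.8 to +16.0 points, and the observed counts give no significant difference anywhere in that range. This rests on two assumptions: that the dosed count lies between completers and randomised in each arm, and that the event counts of 8 and 7 are complete. The second is open for any patient who left before week 8. The correction is worth making because it is standard and cheap and safety is a stated objective, but it does not overturn any conclusion in either document.

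**What to change.** Add one sentence to the SAP defining the safety set as randomised patients who took at least one dose, and say how taking a dose is established. The Protocol says only that a third member of the team hands out the tablets, so if dispensing is the sole record, name it as a proxy. Replace the Table 2 headers with the safety-set number in each arm, which also removes the transposition, and show percentages beside the counts. State per arm how many of the six left before the first dose, between the first dose and the first adverse-event assessment at week 8, and later.

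The cost is a recount from whatever dispensing or visit records exist. The percentages may come out somewhat higher. If the records cannot settle who was dosed, say so and give the range above.
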